5.2.1.2.2 Dose Modification Guidelines for pomalidomide

The recommended starting dose of pomalidomide is 4 mg once daily orally on Days 1-21 of repeated 28-day cycles. Pomalidomide may be taken with water. Inform subjects not to break, chew, or open the capsules. Pomalidomide should be taken without food (at least 2 hours before or 2 hours after a meal).

The criteria presented in this section for dose modification are meant as general guidelines, and they are based on current US standards of clinical practice. Local standards and prescribing information may differ and should be followed. Pomalidomide dose modifications for toxicity must be performed as clinically indicated at the discretion of the investigator. Refer to pomalidomide local prescribing information and [Table 5](#) for dose modification guidelines.

Table 5 Dose Modification Instructions for pomalidomide for Hematologic Toxicities

Toxicity	Dose Modification

Neutropenia
 
 • ANC <500 per mcL or febrile neutropenia (fever more than or equal to 38.5°C and ANC <1,000 per mcL) • ANC return to more than or equal to 500 per mcL • For each subsequent drop <500 per mcL • Return to more than or equal to 500 per mcL 	
 • Interrupt pomalidomide treatment, follow CBC weekly. • Resume pomalidomide treatment at 3 mg daily • Interrupt pomalidomide treatment • Resume pomalidomide treatment at 1 mg less than the previous dose

Thrombocytopenia
 
 • Platelets <25,000 per mcL • Platelets return to >50,000 per mcL • For each subsequent drop <25,000 per mcL • Return to more than or equal to 50,000 per mcL 	
 • Interrupt pomalidomide treatment, follow CBC weekly • Resume pomalidomide treatment at 3 mg daily • Interrupt pomalidomide treatment • Resume pomalidomide treatment at 1 mg less than previous dose

For other Grade 3 or 4 toxicities, hold treatment and restart treatment at 1 mg less than the previous dose when toxicity has resolved to less than or equal to Grade 2 at the physician’s discretion. To initiate a new cycle of pomalidomide, the neutrophil count must be at least 500 per mcL and the platelet count must be at least 50,000 per mcL. If toxicities occur after dose reductions to 1 mg, then discontinue pomalidomide.

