5.11 Clinical Criteria for Early Trial Termination

Early trial termination will be the result of the criteria specified below:

1. Quality or quantity of data recording is inaccurate or incomplete,
2. Poor adherence to protocol and regulatory requirements,
3. Plans to modify or discontinue the development of pembrolizumab.
4. A request made by the U.S. Food and Drug Administration or other similar Health Authority due to safety concerns.

In the event of Sponsor decision to no longer supply pembrolizumab, ample notification will be provided so that appropriate adjustments to subject treatment can be made.

Trial Period:	Screening Phase	Treatment Cycles						End of Treatment		Post-treatment	
		Cycles 1-3 to be repeated beyond 3 cycles									
Treatment Cycle/Title: (28 days cycles)	Screening (Visit 1)	Cycle 1		Cycle 2		Cycle 3		Discon ¹⁵	Post-Treatment Safety Follow-up	Efficacy Follow-up Visits	Survival Follow-up
Cycle Day (visit day) (± 3 days after C1D1 unless otherwise specified)	(-28 to -1 days)	1 (+ 3 days)	22	1	15	1	8	At time of Discon	30 days post Discon	Every 4 weeks post Discon (± 7 days)	Every 12 weeks (± 7 days) or as directed by the Sponsor
Clinical Procedures/Assessments											
Review Adverse Events ²	X	X	X	X	X	X	X	X	X	X	
Full Physical Examination	X	X		X		X		X			
Directed Physical Examination (Arm A)			X		X		X				
Vital Signs and Weight ^{2, 12}	X	X	X	X	X	X	X	X			
12-Lead Electrocardiogram	X										
ECOG Performance Status	X	X		X		X		X			
Skeletal survey	X										
MRI or CT or PET/CT for extramedullary soft tissue plasmacytoma	X										
Disease Response Assessment by IMWG 2011 criteria ¹³		X ¹³		X		X		X	X	X	
Laboratory Procedures/Assessments: analysis performed by local laboratory											
Pregnancy Test – Urine or Serum β-HCG ¹	X	X		X		X		X	X		
Archival or new Bone Marrow Biopsy or Aspirate ⁵	X										
Laboratory Procedures/Assessments: analysis performed by central laboratory											
PT/INR and aPTT	X ³										
CBC with Differential ^{2,13}	X ³	X ¹³	X	X	X	X	X	X	X		
Comprehensive blood Chemistry Panel ^{2,13}	X ³	X ¹³	X	X	X	X	X	X	X		
LDH	X ³					X		X	X		
Urinalysis	X ³					X			X		
T3, (or FT3 per local standard), FT4 and TSH	X ³					X			X		
Serum protein electrophoresis with M-protein quantitation	X	X		X		X		X	X	X ⁴	
Serum immunofixation	X	X		X		X		X	X	X ⁴	
Quantitative Serum Immunoglobulin	X	X		X		X		X	X	X ⁴	
Serum free light chain assay	X	X		X		X		X	X	X ⁴	

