1. For females of child bearing potential two negative pregnancy tests (sensitivity of at least 25mIU/ml) must be obtained within 10-14 days AND within 24 hours prior to C1D1, weekly during Cycle 1 and then monthly in women with regular menstrual cycles, or every 2 weeks in women with irregular menstrual cycles Refer to Section 7.1.5.2 Pregnancy Testing for additional details. 2. Control arm (Arm B) only, measure CBC with differential, comprehensive blood chemistry panel, vital signs, review adverse events, prior and concomitant medications and perform physical exam on Day 1 of each cycle. Subjects in Arm B only need one visit per month on Day 1 of each cycle. For subjects who discontinue pembrolizumab in Arm A, but continue on the study, subsequent visits are also only needed once per month. 3. Safety laboratory tests for screening are to be performed within 10 days prior to the first dose of trial treatment. Safety labs do not need to be repeated on C1D1. See Section 7.1.3 for details regarding laboratory tests. 4. Myeloma laboratory testing should be performed in the follow-up period for all subjects who discontinue study treatment for reasons other than disease progression.											

Trial Period:	Screening Phase	Treatment Cycles						End of Treatment		Post-treatment	
		Cycles 1-3 to be repeated beyond 3 cycles									
Treatment Cycle/Title: (28 days cycles)	Screening (Visit 1)	Cycle 1		Cycle 2		Cycle 3		Discon ¹⁵	Post-Treatment Safety Follow-up	Efficacy Follow-up Visits	Survival Follow-up
Cycle Day (visit day) (± 3 days after C1D1 unless otherwise specified)	(-28 to -1 days)	1 (+ 3 days)	22	1	15	1	8	At time of Discon	30 days post Discon	Every 4 weeks post Discon (± 7 days)	Every 12 weeks (± 7 days) or as directed by the Sponsor

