
5. Bone marrow analysis for all subjects at baseline will include bone marrow morphology, IHC, and Cytogenetics by FISH panel for disease status assessment at local institution. If FISH is not available, then do standard karyotyping. An archival or newly obtained sample may be used at Screening. For subjects (selected sites ONLY) who agree to participate in the optional biomarker sub-study, freshly obtained bone marrow aspirate samples will be collected at C1D1, C2D1 and at time of discontinuation.
 
^a Note: If the subject signs the Future Biomedical Research (FBR) consent, any leftover tissues that would ordinarily be discarded at the end of the trial will be retained for FBR. A copy of the local pathology report, with subject information removed, should also be sent to the lab to accompany the biopsy specimen.
 
6. Pre-dose trough PK and anti-pembrolizumab antibody samples will be collected (Arm A only) at C1D1, C1D22, C2D15, C5D15 and every 4 pembrolizumab infusions thereafter, and 30 days after discontinuation of study drug (or until the subject starts new anti-cancer therapy). Pharmacokinetic/anti-drug antibody (PK/ADA) samples may be used to conduct additional safety analysis, if needed.
 
7. This sample should be drawn for planned analysis of the association between genetic variants in DNA and drug response. If there is either a documented law or regulation prohibiting collection, or if the IRB/IEC does not approve the collection of the sample for these purposes, then this sample will not be collected at that site. If the sample is collected, leftover extracted DNA will be stored for future biomedical research if the subject signs the FBR consent. If the planned genetic analysis is not approved, but FBR is approved and consent is given, this sample will be collected for the purpose of FBR
 
8. Patient reported outcomes (PROs) are assessed on day 1 of every 28-day cycle through Cycle 4 and then every 3 cycles (ie, Cycle 7, 10, 13, etc.) while the subject is receiving study treatment, at treatment discontinuation, and at 30 days post treatment discontinuation (post-treatment safety follow-up)
 
9. Whole blood for correlative studies should only be collected at C1D1, C2D1 and at discontinuation.
 
10. Cycle 1 treatment must be given within 3 days of randomization number assignment in IVRS/IWRS after ensuring subjects meet disease criteria through previous consultation with the Sponsor
 
11. The Pomalidomide Education and Counseling Guidance Document must be completed for all subjects and signed by a trained counselor prior to each dispensing of pomalidomide in accordance with the POMALYST REMS™/country specific risk mitigation program. A copy of this document must be maintained in the subject's records for each dispense for all countries/sites where pomalidomide is provided centrally by the Sponsor.
 
12. Investigational arm (Arm A) should have vital signs measurements on Day 1 of each cycle and on the day of pembrolizumab infusion before and immediately after each administration of the study drug. Weight measurement not required post infusion.
 
13. Disease Response Assessment by IMWG 2011 criteria, CBC with Differential, and Comprehensive blood Chemistry Panel do not need to be performed on Day 1, Cycle 1.
 
14. All subjects enrolled in this study must be able to provide an archived or newly obtained bone marrow biopsy or aspirate sample for minimal residual disease (MRD) characterization by central analysis at screening, at the time of achieving a CR and at 6 months and 1 year after achieving a CR.
 
15. On 03-JULY-2017, the US FDA placed KN183, KN185 and cohort 1 of KN023 on clinical hold based on safety data from KN183 and KN185 presented to the DMC. The FDA determined that the risks of pembrolizumab plus pomalidomide or lenalidomide outweighed any potential benefit for patients with multiple myeloma. Based on this decision, the treatment phase of KN183 and KN185 is closed effective immediately. All subjects must stop study treatment, complete the Discontinuation Visit and move into the long-term safety and survival follow-up per protocol.
 
16. After confirmed disease progression or start of new anti-myeloma therapy, the subject should be contacted approximately every 12 weeks to assess for survival status. Updated survival status may be requested by the Sponsor at any time during the course of the study. Upon Sponsor notification, all subjects who do not/will not have a scheduled study visit or study contact during the Sponsor-defined time period will be contacted for their survival status (excluding subjects who have previously recorded a death event in the collection tool).
											

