
6.1.1 Trial Treatment Administration Schedule

	Each Cycle = 28 Days (Cycles 1-3 To be repeated beyond 3 cycles)											
	Cycle 1				Cycle 2				Cycle 3			
Group A Investigational Arm (Arm A) ^e												
Trial Treatment/ Cycle Day (± 3 days window after C1D1)	Days 1-7 (wk 1)	Days 8-14 (wk 2)	Days 15-21 (wk 3)	Days 22-28 (wk 4)	Days 1-7 (wk 1)	Days 8-14 (wk 2)	Days 15-21 (wk 3)	Days 22-28 (wk 4)	Days 1-7 (wk 1)	Days 8-14 (wk 2)	Days 15-21 (wk 3)	Days 22-28 (wk 4)
Pembrolizumab (Q3W) ^a	1			22			15			8		
Pomalidomide ^b	1 to 21				1 to 21				1 to 21			
Dexamethasone ^c	1	8	15	22	1	8	15	22	1	8	15	22
Pill count for Pomalidomide and Dexamethasone ^d	1				1				1			
Group B Control Arm (Arm B) ^e												
Pomalidomide ^b	1 to 21				1 to 21				1 to 21			
Dexamethasone ^c	1	8	15	22	1	8	15	22	1	8	15	22
a) Pembrolizumab will be administered as 200 mg every 21 days (3 weeks) as an IV infusion over 30 minutes. b) Pomalidomide will be administered as 4 mg PO, once daily on Days 1 to 21 of repeated 28-day cycles. Pomalidomide must be prescribed through and in compliance with the POMALYST REMS™ program or refer to local prescription drug label. c) Low dose dexamethasone will be administered as 40 mg PO, once daily on Days 1, 8, 15 and 22 of repeated 28-day cycles. A low dose dexamethasone dose of 20 mg on Days 1, 8, 15 and 22 in subjects aged > 75 years is recommended. Refer to the local prescription drug label. d) Site should document drug accountability as per their institutional guidelines. e) On 03-JULY-2017, the US FDA placed KN183, KN185 and cohort 1 of KN023 on clinical hold based on safety data from KN183 and KN185 presented to the DMC. The FDA determined that the risks of pembrolizumab plus pomalidomide or lenalidomide outweighed any potential benefit for patients with multiple myeloma. Based on this decision, the treatment phase of KN183 and KN185 is closed effective immediately. All subjects must stop study treatment, complete the Discontinuation Visit and move into the long-term safety and survival follow-up per protocol.												

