7.1.3.1 Laboratory Safety Evaluations (Hematology, Chemistry and Urinalysis)

Laboratory tests for hematology, chemistry and urinalysis are specified in [Table 12](#).

Table 12 Laboratory Tests

Hematology^f	Chemistry	Urinalysis	Other
Hematocrit	Albumin	Blood	Serum β -human chorionic gonadotropin (β -hCG) ^a
Hemoglobin	Alkaline phosphatase	Glucose	PT (INR) ^d
Platelet count	Alanine aminotransferase (ALT)	Protein	aPTT ^d
WBC (total and differential)	Aspartate aminotransferase (AST)	Specific gravity	Total Triiodothyronine (T3) ^e
Red Blood Cell Count	Calcium	Microscopic exam, if abnormal results are noted	Free thyroxine (free T4)
Absolute Neutrophil Count	Bicarbonate/Carbon dioxide ^b	Urine pregnancy test ^a	Thyroid stimulating hormone (TSH)
Absolute Lymphocyte Count			Blood for FBR
	Chloride		Blood for Proteomics
	Creatinine		Blood for Genetics
	Glucose		Blood for Transcriptional Analysis
	Phosphorus		
	Potassium		
	Sodium		
	Total Bilirubin		
	Direct Bilirubin, if total bilirubin is elevated above ULN		
	Total protein		
	Blood Urea Nitrogen		
	Uric acid		
	Urea ^c		

a. Perform on women of childbearing potential only. Urine pregnancy test is preferred. If the urine test is positive or cannot be confirmed as negative, a serum pregnancy test will be required.

b. Test only if part of Standard of Care locally.

c. Blood Urea Nitrogen is preferred; if not available urea may be tested.

d. Coagulation factors (PT/INR and aPTT) should be tested as part of the screening procedures for all subjects. Any subject receiving anticoagulant therapy should have coagulation factors monitored closely throughout the trial.

e. Total T3 is preferred, if not available free T3 may be tested.

f. Absolute values or percentage per central laboratory.

All laboratory tests will be performed by a central laboratory on day 1 of each cycle and previous to pembrolizumab infusions for the investigational arm (Arm A). Specific laboratory tests may be performed locally, in parallel to central laboratory tests, at the investigator discretion to ensure subject's safety prior to treatment. Laboratory tests for screening should be performed within 10 days prior to the first dose of treatment. Safety labs do not need to be repeated on C1D1. After Cycle 1, pre-dose laboratory procedures can be conducted up to 72 hours prior to dosing. Results must be reviewed by the investigator or qualified designee and found to be acceptable prior to each dose of trial treatment

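### While on pembrolizumab, Arm A has blood counts, chemistry and AE review scheduled twice as often as Arm B, and Section 8.6.2 as reviewed does not account for this when comparing short-lived laboratory AEs (minor)

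*Combined protocol and SAP*

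**What the plan says.** **Schedule.** The Trial Flow Chart (Section 6.1) marks CBC, chemistry and AE review at C1D1, C1D22, C2D1, C2D15, C3D1 and C3D8, and this three-cycle pattern repeats. Footnote 2 restricts Arm B to the Day 1 columns: "Subjects in Arm B only need one visit per month on Day 1 of each cycle". The difference ends when pembrolizumab ends: "For subjects who discontinue pembrolizumab in Arm A, but continue on the study, subsequent visits are also only needed once per month". Section 7.1.3.1 agrees with the flow chart: laboratory tests are done "by a central laboratory on day 1 of each cycle and previous to pembrolizumab infusions for the investigational arm". Footnote 13 waives the first sample in both arms: "CBC with Differential, and Comprehensive blood Chemistry Panel do not need to be performed on Day 1, Cycle 1".

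**What is not affected.** The row "T3, (or FT3 per local standard), FT4 and TSH", like those for LDH and urinalysis, has its only on-treatment mark at C3D1. The myeloma tests fall on Day 1. These are the same in both arms.

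**Analysis.** Section 8.6.2 compares the percentage of subjects with each AE using Miettinen and Nurminen 95% intervals (Tier 2), and time to first Grade 3-5 AE using an unstratified log-rank test and Cox model. It calls the Tier 2 intervals descriptive and the time-to-event analysis exploratory. The one related adjustment it names is an optional exposure-adjusted incidence density, intended for unequal follow-up time. Further detail on time to Grade 3-5 AE is left to a supplemental SAP. Section 8.6.1 does provide sensitivity analyses for unequal assessment schedules, but only for PFS.

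**The concern.** A neutropenia or transaminase rise that comes and goes between two samples is recorded only if something else brings it to light. Arm A has twice as many scheduled chances to find it, so its AE percentage can be higher, and its time to first event shorter, with no difference in true risk.

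Timing differs as well as number. Section 6.1.1 states: "Pomalidomide will be administered as 4 mg PO, once daily on Days 1 to 21 of repeated 28-day cycles". Arm A's extra samples fall on Days 8, 15 and 22, during or just after dosing. Arm B's on-treatment samples fall only on Day 1, after the off-drug week. The first scheduled on-treatment CBC is on Day 22 in Arm A and Day 29 in Arm B.

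Incidence density does not remove this. It divides by time on treatment, and the arms differ in tests per unit of time. At stake is how the CBC and chemistry AE rows are read: part of an Arm A excess could come from the schedule, and the planned tables would not show how much.

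**Working it through.** **Count.** Infusion days are 1 + 21i and cycle Day 1s are 1 + 28j. The pattern repeats every 84 days (3 × 28 = 4 × 21). After Day 1, Arm A is sampled on days 22, 29, 43, 57, 64 and 85, and Arm B on days 29, 57 and 85. That is 6 v 3, which reproduces the flow chart columns. Counted from C1D1 up to but not including C4D1, the waiver leaves 5 v 2 laboratory samples in the first block; AE review stays 6 v 3.

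**Detection, onset on any day (assumed).** The gaps are 21, 7, 14, 14, 7, 21 days in Arm A and 28, 28, 28 in Arm B. The chance that an episode of L days meets a scheduled sample is Σ min(gap, L)/84.

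| Episode length | Arm A | Arm B |
|---|---|---|
| 7 days | 42/84 = 50% | 21/84 = 25% |
| 10 days | 54/84 = 64% | 30/84 = 36% |
| 14 days | 70/84 = 83% | 42/84 = 50% |
| 21 days | 84/84 = 100% | 63/84 = 75% |
| 28 days | 100% | 100% |

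The mean wait from onset to the next sample is Σ gap²/(2 × 84): 1372/168 = 8.2 days v 2352/168 = 14.0 days. Simulating the ±3-day visit windows, with samples up to 72 hours early, moves each detection figure by about 4 points at most (at 28 days, 100% v 96%).

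**Detection, onset on Days 8-22 of a cycle (assumed).** Averaged over the three cycles: 33% v 0% at 7 days, 55% v 21% at 10 days, 83% v 50% at 14 days, and 100% in both arms from 21 days.

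**Size in percentage points (illustration only).** Excess = risk × (detection in A − detection in B) × (1 − share found otherwise). Section 4.2.2.2 reports Grade 3 or higher cytopenias from 8% (thrombocytopenia) to 29% (neutropenia) in 24 patients. I use 29% as an assumed equal risk in both arms.

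- One episode per affected subject, nothing found otherwise, onset on any day: 29 × 0.25 = 7.3 points at 7 days, 29 × 0.333 = 9.7 at 14 days, 29 × 0.25 = 7.3 at 21 days, 0 from 28 days.
- The same with onset on Days 8-22: 29 × 0.333 = 9.7 points at 7 and 14 days, 0 from 21 days.
- Two independent episodes, onset on any day: 29 × [(1 − b)² − (1 − a)²], where a and b are the detection chances in Arms A and B, gives 29 × 0.3125 = 9.1, 29 × 0.2222 = 6.4 and 29 × 0.0625 = 1.8 points at 7, 14 and 21 days.
- If half are found otherwise, each figure halves; if three quarters are, each falls to a quarter.
- At 8% risk (one episode, onset on any day) the figures are 2.0 to 2.7 points for 7- to 21-day episodes.

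**What a Day 1 analysis would find.** Both arms then have Arm B's detection: 25%, 36%, 50%, 75% and 100% at 7, 10, 14, 21 and 28 days with onset on any day, but 0% at 7 days and 21% at 10 days with onset on Days 8-22. As a worst case, suppose every cytopenia found at C2D15 or C3D8 clears before the next Day 1. Arm A then loses 7/84 at 21 days (56/84 = 67% v 75%) and 21/84 at 28 days (63/84 = 75% v 100%), and nothing up to 14 days. C1D22 falls after the last pomalidomide day of the cycle, so interruption there changes nothing before the next Day 1.

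**The case against.** **Nothing confirmatory depends on it.** There are no Tier 1 events, and no alpha or decision rule is attached to these analyses. The extra visits come with the infusions, and the flow chart states them openly. This stands, and it is why the point is minor.

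**Other detection may close much of the gap.** Section 7.1.3.1 allows local tests in both arms: "Specific laboratory tests may be performed locally, in parallel to central laboratory tests, at the investigator discretion". Section 5.2.1.2.2 directs investigators to local prescribing information and local standards for pomalidomide, and any CBC monitoring set there would apply in both arms. The documents do not give that text, so the share found otherwise is unknown. This stands and limits what can be said about size. The Table 5 instruction "Interrupt pomalidomide treatment, follow CBC weekly" helps less, because it starts only after a cytopenia has been found.

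**The risk input is weak.** The 8% to 29% range comes from 24 patients, all on the three-drug combination, and the sampling schedule is not given. These are observed rates, not true or control-arm risks. This stands.

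**The Day 1 analysis is nearly blind to the events at issue, and leans against an Arm A excess.** It finds none of the 7-day episodes with onset on Days 8-22. This stands: the analysis can only be supportive.

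**Stronger readings to avoid.** A reader might infer that an Arm A safety excess, or the basis for the clinical hold, reflects extra testing. The documents do not support that. AEs are reported continuously in both arms (Section 7.2), and deaths, SAEs and symptomatic AEs do not depend on a scheduled blood sample in the same way. A reader might also infer that the sponsor has no analysis for this anywhere. The supplemental SAP was not among the documents, and Section 8.0 says the analysis may be modified and reported in the CSR, so the statement holds only for Section 8.6.2 as reviewed.

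**Conclusion.** The point holds as a minor matter of interpretation. The schedule difference is certain: 6 v 3 per 84 days while Arm A is on pembrolizumab, and equal afterwards. At equal true risk it makes short-lived CBC and chemistry AEs more likely to be detected, and detected earlier, in Arm A, if symptoms or other tests do not find them.

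Confidence in the size is moderate only. The detection figures rest on assumed onset patterns. The range of 0 to about 10 points also assumes a 29% risk, one episode per affected subject and no other detection; it includes nil from 21 days with onset on Days 8-22, and two episodes change the pattern. No single figure in percentage points should be quoted as the bias. The effect on time to first Grade 3-5 AE of any kind is further diluted by clinical events.

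**What to change.** Keep the all-records tables as the main safety analysis. Add to Section 8.6.2, or to the analysis description in the CSR:

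> As a supportive analysis, CTCAE-graded central CBC and chemistry results, and time to first Grade 3-4 abnormality in these tests, will be compared between arms using only Day 1 assessments from Cycle 2 onward. The difference in assessment schedule will be stated beside the all-records laboratory AE results.

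Treatment closed in July 2017, so the analysis should be labelled post hoc in the CSR.

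The cost is a short text addition and a little programming on central laboratory data already collected; no visits are added. State the limits with the result: the low Day 1 yields shown above, and possible understatement of Arm A when a mid-cycle finding leads to interruption. The all-records results lean toward an Arm A excess and the Day 1 results lean against one, so they must be read together. The Day 1 analysis does not isolate the schedule effect on its own, and it must not be used to discount the Arm A safety findings. If only one part is adopted, the statement beside the tables is the more useful.
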